9.3. Vaccine accountability and disposal

On completion of the trial and of close-out monitoring visits to check vaccine accountability, at the request of the CI, any remaining vials of investigational vaccines held in Uganda will either be shipped back to the Sponsor or will be destroyed by the National Drug Authority, and a certificate of shipment or destruction will be obtained as applicable.

10. ASSESSMENT OF SAFETY

Safety will be assessed by the frequency, incidence and nature of adverse events and serious adverse events arising during the trial.

10.1. Interim Safety Review

Prior to dose escalation of the IMP or age de-escalation, the clinical team and Chief Investigator will review the safety data and adverse events in volunteers before proceeding to the next group.

Dose escalation or age de-escalation will not take place in the event of any of the holding criteria being met. In addition, the Phase IIa randomised trial will be held, and the DSMB will be consulted, if any of the following holding criteria occurs.

10.1.1. Holding criteria

Safety holding rules would be activated by any of the following:

- **A serious adverse event considered possibly, probably or definitely related to vaccination occurs**
- **Death occurs**
- **A life-threatening reaction occurs**
- **Solicited systemic adverse events:**

If 2 or more vaccinations in group 1, 2, 3 or 4; or more than 25% of doses of the vaccine in group 5; is followed by the same Grade 3 solicited systemic adverse event beginning within 2 days after vaccination (day of vaccination and one subsequent day) and persisting at Grade 3 for >48hrs.

- **Unsolicited adverse events:**

If 2 or more vaccinations in group 1, 2, 3 or 4; or more than 25% of doses of the vaccine in group 5; develop the same Grade 3 unsolicited adverse event beginning within 7 days after vaccination that is considered related to vaccination and persists at Grade 3 for > 48 hours.

- **Laboratory adverse event:**

If 2 or more vaccinations in group 1, 2, 3 or 4; or more than 25% of doses of the vaccine in group 5; develop the same Grade 3 laboratory adverse event beginning within 7 days after vaccination and persists at Grade 3 for > 48 hours.

If a holding rule has been met, the internal safety review will consider:

- The relationship of the AE or SAE to the vaccine.
- The relationship of the AE or SAE to the vaccine dose, or other possible causes of the event.
- If appropriate, additional screening or laboratory testing for other volunteers to identify those who may develop similar symptoms and alterations to the current Volunteer Information Sheet (PIS).
- New, relevant safety information from ongoing research programs on the various components of the vaccine.

The local ethics committee and vaccine manufacturers will also be notified if a holding rule is activated or released.

All vaccinated volunteers will be followed for safety until the end of their planned participation in the study or until resolution or stabilisation (if determined to be chronic sequelae) of their AEs, providing they consent to this.

In addition to these pre-defined criteria, the study can be put on hold upon advice of the Chief Investigator, Principal Investigator, Study Sponsor, Regulatory Authority, Ethical Committee(s) or DSMB, for any single event or combination of multiple events which, in their professional opinion, jeopardise the safety of the volunteers or the reliability of the data.

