3.2. Schedule of visits and procedures for groups 1-4

Visit number	1	2	3	4	5	6	7
Timeline (days)*	Screening	0	2	14	28	56	168
Timeline (weeks)*		0		2	4	8	24
Time windows (days)	-90 to -7		+1	+3	+5	+5	+14
Vaccination, ChAdOx1 85A		x					
Inclusion/exclusion criteria	x	x					
Review contra-indications	x	x					
Informed consent	x						
Medical history	x	(x)	(x)	(x)	(x)	(x)	(x)
Physical examination	x	(x)	(x)	(x)	(x)	(x)	(x)
Vital signs	x	x	x	x	x	x	x
Urinalysis	x						
β-HCG urine test (female only)	x	x					
Stool parasitology	x	x	x				x
Anthelmintic treatment						x	
Local & systemic events/reactions		x	x	x	x	x	x
Diary cards provided		x					
Diary cards collected				x			
Biochemistry (4mL)**/***	x			x			
HBV, HCV, HIV (6mL)	x						
Haematology: full blood count and storage (2mL)	x		x	x			
Mansonella perstans (1mL)***	x						x
Malaria RDT/slide; PCR (1mL)	x	x***		x	x		x
Assessments of immunogenicity and exploratory immunology incl ELISpot (10-20mL)****	x	x	x	x	x	x	x
Gene expression (2mL)	x		x				
Blood vol (mL)	36	0	6	28	9	5	24
Cumulative blood vol (mL)	36	36	42	70	79	84	108

X Event scheduled to occur

(X) If considered necessary, emphasising any complaint or change in medications

* Timeline is approximate only, as exact timings (\pm windows periods) of visits relate to the actual (not intended) date of the previous visit

** Urea & electrolytes, liver function tests

*** Repeated on vaccination day if delay from screening is more than 28 days

**** Exploratory immunology blood volume will be guided by guidelines from Harvard Mass General, where a maximum of 3ml/kg body weight is taken at any one time point and not more than 3ml/kg is taken over any 8 week period (ref http://www.drgreene.com/21_1616.html.) These guidelines have been followed in previous studies vaccinating adolescents and children with MVA85A (in South Africa [1]). The total blood volume planned is 84 ml over the initial intensive sampling period of 8 weeks. Revision of sample volumes based on weight will only be required for children who weigh less than 28 kg; the average weight of children aged 11 is expected to be greater than 35kg, with greater weights for older children.

Table 1.1. Schedule of trial procedures groups 1-4

Schedule of visits and procedures for groups 5 and 6

Visit number	1	2	3	4	5	6	7	8	9	10
Timeline (days)*	Screening	0	2	14	28	56- 365 ^a	63- 372 ^a	84- 393 ^a	140- 449 ^a	224- 533 ^a

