Timeline (weeks)*		0		2	4	8-52	9-53	12-56	20-64	32-76
Time windows (days)	-90 to -7		+1	+3	+5	+5	+1	+5	+5	+14
Vaccination, ChAdOx1 85A or BCG		x								
Vaccination, MVA85A [§]						x [§]				
Inclusion/exclusion criteria	x	x								
Review contra- indications	x	x				x				
Informed consent	x									
Medical history	x	(x)	(x)	(x)	(x)	(x)	(x)	(x)	(x)	(x)
Physical examination	x	(x)	(x)	(x)	(x)	(x)	(x)	(x)	(x)	(x)
Vital signs	x	x	x	x	x	x	x	x	x	x
Urinalysis	x									
β-HCG urine test (female only)	x	x				x				
Stool parasitology	x	x	x							x
Anthelminthic treatment									x	
Local & systemic events/reactions		x	x	x	x	x	x	x	x	x
Diary cards provided		x				x				
Diary cards collected				x			x			
Biochemistry (4mL)**/***	x			x		x	x			
HBV, HCV, HIV (6mL)	x									
Haematology: full blood count and storage (2mL)	x		x	x		x	x		x	x
Mansonella perstans (1mL)***	x									x
Malaria RDT/slide; PCR (1mL)	x	x***		x	x	x		x		x
Assessments of immunogenicity and exploratory immunology incl ELISpot (10-20mL)****	x	x	x	x	x	x	x	x	x	x
Gene expression (2mL)	x		x							
Blood vol (mL)	26	10	16	28	5	13	28	5	5	24
Cumulative blood vol (mL)	26	36	52	80	85	98	126	131	136	160

X Event scheduled to occur

(X) If considered necessary, emphasising any complaint or change in medications

* Timeline is approximate only, as exact timings (\pm windows periods) of visits relate to the actual (not intended) date of the previous visit

§ Group 5 only

** Urea & electrolytes, liver function tests

*** Repeated on vaccination day if delay from screening is more than 28 days

**** Exploratory immunology blood volume will be guided by guidelines from Harvard Mass General, where a maximum of 3ml/kg body weight is taken at any one time point and not more than 3ml/kg is taken over any 8 week period (ref http://www.drgreene.com/21_1616.html.) These guidelines have been followed in previous

studies vaccinating adolescents and children with MVA85A (in South Africa [1]). The total blood volume planned is 98 ml over the initial intensive sampling period of 8 weeks. Revision of sample volumes based on weight will only be required for children who weigh less than 33 kg; the average weight of children aged 11 is expected to be greater than 35kg, with greater weights for older children.

a Participants will have variable follow up days depending on whether they were enrolled before or after the COVID 19 lockdown

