5.4. Risks and Benefits

5.4.1. Potential risks

The potential risks to volunteers in this trial include risks associated with:

1. Venepuncture

Localised bruising and discomfort can occur at the site of venepuncture. Infrequently fainting may occur. The total volume of blood drawn over a 6-month period will be 160mL, which should not compromise these otherwise healthy volunteers.

2. Vaccination

ChAdOx1 85A has been administered to 42 healthy UK adults with no SAEs or safety concerns. MVA85A has now been administered to over 2500 healthy human individuals with one possible serious adverse reaction (SAR). BCG is a licensed vaccine which has been administered to millions of people. The potential known adverse events associated with vaccination are:

Local reaction from IM vaccination

The typical local reaction as a result of IM injection is temporary pain, redness and swelling at the site of the injection.

Local reaction for intradermal (ID) vaccination

BCG vaccination or revaccination usually causes local scarring and occasionally an abscess and regional lymphadenopathy [52].

Systemic reactions

Constitutional influenza-like symptoms such as fatigue, headache, malaise, feverishness, and muscle aches can occur with any vaccination and last for 2-3 days. In the case of MVA85A, and ChAdOx1 85A these are usually mild to moderate in severity, and transient. Following ChAdOx1 85A vaccination in TB034, transient lymphopenia and neutropenia was seen in some volunteers; all spontaneously resolved. Similar mild to moderate transient abnormalities of leukocyte parameters have been previously noted in other adenovectored vaccine studies [24, 53].

Presyncopal and syncopal episodes may occur at the time of vaccination which rapidly resolve. As with any other vaccine, immune mediated reactions that can lead to organ damage may occur. For influenza vaccines an excess of approximately 1 Guillain-Barré syndrome case per million persons immunised has been observed. No cases were observed in people under 45 years of age. However, this has never been seen with the ChAdOx1 85A or MVA85A vaccines or vaccines containing any of its components. In immunocompromised people, BCG vaccination can cause disseminated disease [54, 55].

Allergic reactions

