7. TRIAL DESIGN

We will commence with a dose-escalation and age de-escalation study in healthy adults and adolescents in Uganda, focussing on ChAdOx1 85A, to provide safety data for ChAdOx1 85A in this population. These measures are not required for MVA85A since this vaccine has been more widely used, including among adolescents in Uganda, and the dose has been standardised (as described above).

ChAdOx1 85A dose escalation and age de-escalation will be followed by a Phase IIa randomised trial comparing the immunogenicity of ChAdOx1 85A and MVA85A with the immunogenicity of BCG revaccination. ChAdOx1 85A and MVA85A will be administered via the intramuscular route. The target dose for the Phase IIa trial is 2.5×10^{10} vp because the lower dose is expected to have lower immunogenicity, based on the Oxford study, TB034 (Table 3, above). Data from the Oxford study suggest that this dose will be well tolerated. However, if this dose is not tolerated then the lower dose will be used. The dose of MVA85A will be 1×10^8 pfu in the groups in which it is given.

There will be 6 study groups with 3 to 30 volunteers in each group (Table 5).

Dose escalation for ChAdOx1 85A in adults

Group 1. The first three adults will receive ChAdOx1 85A at 5×10^9 vp.

Group 2. The next three adults will be enrolled after safety data has been reviewed by the trial management team to one week after ChAdOx1 85A vaccination in group 1. These adults will receive ChAdOx1 85A at 2.5×10^{10} vp.

Age de-escalation and dose escalation for ChAdOx1 85A in adolescents

Group 3. The first three adolescents will be enrolled after safety data has been reviewed to one week after ChAdOx1 85A vaccination in group 2. These three adolescents will receive ChAdOx1 85A at 5×10^9 vp

Group 4. The next three adolescents will be enrolled after safety data has been reviewed to one week after ChAdOx1 85A vaccination in group 2. These three adolescents will receive ChAdOx1 85A at 2.5×10^{10} vp

Randomised comparison of ChAdOx1 85A-MVA85A versus BCG revaccination

Once safety data has been reviewed for groups 1 to 4 to one week post ChAdOx1.85A vaccination, recruitment to the randomised trial will commence. Sixty adolescents will be randomised, 30 (group 5) to receive ChAdOx1 85A at 2.5×10^{10} vp followed by MVA85A boost and 30 (group 6) to receive BCG revaccination.

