7.9. Timepoints

Screening – trial enrolment time window

Enrolment should take place no longer than 90 days following the date of screening appointment. If more than 90 days elapse, the screening visit should be repeated in full prior to enrolment in order to minimise the risk to volunteers of any new unidentified health problems having arisen during that period.

Vaccination of first volunteer – subsequent vaccination time window

The first volunteer, who will be allocated to Group 1, will be vaccinated with ChAdOx1 85A by the intramuscular route at least 7 days before any subsequent volunteers in this group. After safety review by the clinical team and the Chief Investigator of the three Group 1 volunteers, the first volunteer in Group 2 will be vaccinated at least 7 days prior to further volunteer enrolment into Group 2. After similar safety review of the three Group 2 volunteers, the first volunteer in Group 3 will be vaccinated at least 7 days prior to further enrolment into Group 3. After similar safety review of the three Group 3 volunteers, the first volunteer in Group 4 will be vaccinated at least 7 days prior to further enrolment into Group 4. After review by the clinical team and the Chief Investigator of the safety data from groups 1-4, enrolment into the randomised trial will commence. The data and safety monitoring board (DSMB) will be consulted if there are any issues of concern.

Follow up period

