8.3. Blood tests, urine and stool analysis

Blood will be drawn for the following laboratory tests and processed at the EMaBS clinic laboratory, or in laboratories at the Uganda Virus Research Institute (UVRI), using standard procedures:

- **Haematology and haemoparasitology:** full blood count, malaria slide, *Mansoniella perstans* (using modified Knott's method [59]); malaria PCR will be conducted for sub-microscopic parasitaemia.

- **Biochemistry:** Sodium, Potassium, Urea, Creatinine, Albumin, Liver Function Tests (ALT, ALP, GGT)
- **Diagnostic serology:** HBsAg, HCV antibodies, HIV antibodies (specific consent will be gained prior to testing blood for these blood-borne viruses)
- **Exploratory Immunology:** Immunogenicity will be assessed by a variety of immunological assays. This includes *ex vivo* ELISpot assays for interferon gamma and flow cytometry assay. Other exploratory immunological assays including cytokine analysis and gene expression studies amongst others may be performed at the discretion of the Investigators. Immunological assays will be conducted according to local SOPs.
- **Urinalysis:** Urine will be tested for protein, blood and glucose at screening. For female volunteers only, urine will be tested for beta-human chorionic gonadotropin (β -HCG) at screening and immediately prior to vaccination. Urine will also be examined for circulating cathodic antigen of *Schistosoma* species.
- **Stool:** stool samples will be examined for helminths by the Kato Katz method, and by PCR [60]. A sample will be stored for possible analysis of the microbiome in future.

Genetic studies, including a genome wide association analysis and work on HLA typing, have already been undertaken among EMaBS participants, based on prior ethical approval and consent. Genetic analyses relevant to vaccine responses were the primary motivation for the work. This will provide the opportunity for genetic analyses using immunological data generated under this new protocol also.

Collaboration with other specialist laboratories in the UK, Europe and outside of Europe for further exploratory tests may occur. This would involve the transfer of serum, urine or plasma and/or PBMC to these laboratories, but these would remain anonymised. Informed consent for this will be gained from volunteers. A Material Transfer Agreement will be submitted for review and approval before any samples are sent to collaborating institutions.

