10.7. Procedures to be followed in the event of abnormal findings

Eligibility for enrolment in the trial in terms of laboratory findings will be assessed as detailed in Section 7. Abnormal clinical findings from medical history, examination or blood tests will be assessed as to their clinical significance throughout the trial. Laboratory adverse events will be assessed using the normal ranges based on those defined locally by Lugada and colleagues for haematology [61], and those provided by the ISO accredited Clinical Diagnostic Laboratory at UVRI for biochemistry. If a test is deemed clinically significant, it may be repeated, to ensure it is not a single occurrence. If a test remains clinically significant, the volunteer will be informed and appropriate medical care arranged as appropriate and with the permission of the volunteer. Specific details regarding findings, discussion with volunteers and resulting actions will be recorded in the CRF. Decisions to exclude the volunteer from enrolling in the trial or to withdraw a volunteer from the trial will be at the discretion of the Investigator.

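### After ChAdOx1 85A the first scheduled chemistry is at day 14, so the 7-day laboratory holding rule cannot work on chemistry for any of the 42 prime doses

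*Combined protocol and SAP*

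**What the plan says.** Section 10.1.1 lists the events that stop escalation or put the randomised trial on hold. The laboratory criterion is met in group 5 when "more than 25% of doses of the vaccine in group 5; develop the same Grade 3 laboratory adverse event beginning within 7 days after vaccination", provided that the event stays at Grade 3 for more than 48 hours. In groups 1-4 two vaccinations are enough, under the same timing conditions.

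The sampling times are in the schedules in sections 3.2 and 3.3:

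- **Chemistry** (row "Biochemistry (4mL"): groups 1-4 at screening and day 14 only. Groups 5 and 6 at screening, day 14, the boost visit and 7 days after the boost. A footnote adds a vaccination-day sample when screening was more than 28 days earlier. Under section 8.3 the panel covers electrolytes, urea, creatinine, albumin and "Liver Function Tests (ALT, ALP, GGT").
- **Blood count** (row "Haematology: full blood count and storage (2mL"): all groups at screening, day 2 and day 14. Groups 5 and 6 also at the boost visit, 7 days after it, and at the last two visits.

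The day-2 visit has a window of ±1 day, the day-14 visit ±3 days and the visit 7 days after the boost ±1 day. Section 10.7 says of a clinically significant result that "it may be repeated, to ensure it is not a single occurrence". It sets no time for the repeat and does not require one.

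**The concern.** To apply the rule to a laboratory value, the team needs one Grade 3 result that can be dated to the first 7 days and a second one more than 48 hours later. For chemistry after ChAdOx1 85A the schedule provides no sample in the first 7 days, so the first condition cannot be checked.

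The rule exists to catch changes that cause no symptoms, such as a rise in liver enzymes. If such a rise occurred in many adolescents in the first 10 days after the prime and then resolved, a team following the plan exactly would see nothing. If it was still present at day 14, the result would be known but would not meet the rule. In both cases a safety report could state that the laboratory criterion was not met when it could not have been tested. ChAdOx1 85A is the newer of the two products: section 5.4.1 puts prior exposure at 42 UK adults, against more than 2500 people for MVA85A. Yet only MVA85A has chemistry scheduled one week after the dose.

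**Working it through.** **Inputs.** The rule is from section 10.1.1. Visit days, windows and blood volumes are from sections 3.2 and 3.3. Group sizes are from section 7.1. The plan gives no figure of its own to reproduce on this point.

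**Chemistry after ChAdOx1 85A.** Planned prime doses are 4 × 3 + 30 = 42. The earliest scheduled sample is day 14 − 3 = 11. If windows run from the actual date of an early day-2 visit, it is (2 − 1) + (14 − 2) − 3 = day 10. Both are later than day 7. The footnoted vaccination-day sample is a baseline and does not help. Doses with a scheduled chemistry sample that could date onset to days 0-7: 0 of 42. Counting this product alone, group 5 needs floor(0.25 × 30) + 1 = 8 events. The number that can be documented is 0 whatever the true rate.

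**Chemistry after MVA85A.** Samples are taken on the boost day and at 7 ± 1 days. Taking the boost-day sample as drawn before the injection, onset is bracketed. No later chemistry is scheduled, so persistence depends on the optional repeat.

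**Blood count.** After the prime, the day-2 and day-14 samples are (14 − 3) − (2 + 1) = 8 to (14 + 3) − (2 − 1) = 16 days apart. After the boost, the next count following the 7-day sample is 140 − 63 = 77 days later on the nominal schedule.

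**How much the sampling sees after the prime.** The documents give neither onset times nor durations. I assume onset t uniform over days 0-7, fixed duration D and nominal visit days. A sample at day s with a repeat g days later documents the event if t ≤ s and t + D ≥ s + g.

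- Blood count, scheduled samples only: needs t ≤ 2 and t + D ≥ 14. This gives 0% for D = 3, 5, 7 or 10, and 2/7 = 29% for D = 14.
- Blood count with the optional repeat 48 hours after day 2: needs t ≤ 2 and t + D ≥ 4. This gives 1/7 = 14% for D = 3, and 2/7 = 29% for D = 5, 7 or 10.
- Chemistry under the current rule: 0% for every D.

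**Chemistry under the fix below** (samples at days 2 and 14, mandatory repeat at 48 or 96 hours, events with onset in days 0-7):

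| Duration | Repeat at 48 h | Repeat at 96 h |
|---|---|---|
| 7 days | 2/7 + 0 = 29% | 2/7 + 0 = 29% |
| 10 days | 2/7 + 1/7 = 43% | 2/7 + 0 = 29% |
| 14 days | 2/7 + 5/7 = 100% | 2/7 + 3/7 = 71% |

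The first term is the day-2 sample and the second the day-14 sample.

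**What this does to the hold.** The documents give no event rate, so a range of true rates p is assumed. With all 30 group 5 primes complete, P(Bin(30, p) ≥ 8) is 24%, 72% and 96% for p = 20%, 30% and 40% if every event is seen. Under the current rule it is 0% for chemistry at every rate. Under the fix, with p multiplied by the capture fraction:

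- 7-day events (2/7): 0.02%, 0.3% and 1.7%.
- 14-day events, repeat at 96 hours (5/7): 5.5%, 31% and 66%.
- 14-day events, repeat at 48 hours: the full 24%, 72% and 96%.

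**Blood volume.** 98 + 4 = 102 mL over the first 8 weeks. 102 / 3 = 34 kg, against 98 / 3 = 32.7 kg now (33 in the text).

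**The case against.** Much of the opposing case stands. A related SAE, a death or a life-threatening reaction triggers a hold by itself, and several parties, including the DSMB, may stop the trial at discretion. A Grade 3 value at day 14 would reach the investigators and could prompt such a hold. Section 5.1.5 reports only haematological laboratory events related to vaccination in the UK study, so a chemistry signal is hypothetical. These points limit the consequence. They do not make the written rule testable on chemistry after the prime.

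Three stronger readings are tempting, and the documents do not support them.

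- *No dose of either product could ever count.* Not so for MVA85A. Onset is bracketed there, section 10.7 permits a repeat, and section 10.1.1 follows vaccinated volunteers to the end of planned participation or until their AEs resolve or stabilise. What is missing is an obligation to repeat within a set time.
- *The rule is dead for blood counts too.* Counts on days 2 and 14 can satisfy it after the prime. Section 5.4.1 says that "transient lymphopenia and neutropenia was seen in some volunteers; all spontaneously resolved" and likens these to mild or moderate changes with similar vectors, so missing them is not a failure of a Grade 3 rule. Section 10.6 also grades laboratory events as multiples of the limit of normal and does not say how falls are graded, so the capture figures for low counts are only indicative.
- *Escalation went ahead blind to chemistry.* Section 7.9 describes participants already enrolled before the lockdown and awaiting MVA85A, so group 5 had opened and no change now can affect those steps. With the 7-day stagger within each group, the earliest start of the randomised part would also have had day-14 chemistry due for all of groups 1-3 and the first volunteer of group 4, which is 9 + 1 = 10 of 12. Section 10.8 requires DSMB reports before group 3 and before randomisation.

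**Conclusion.** The mismatch is real and follows from the rule and the two visit tables alone. For chemistry after ChAdOx1 85A the laboratory holding rule cannot be met as written, for any of the 42 planned doses and at any event rate. Repeating the day-14 test does not cure this. After MVA85A the defect is limited to persistence and is removed by a mandatory repeat. For blood counts after the prime, the rule can see only events present at the day-2 sample and still Grade 3 on a repeat or at day 14.

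The capture percentages rest on assumed uniform onset and fixed durations, and the hold probabilities on assumed event rates. The finding that no prime dose can count on chemistry rests on none of these. The gap is confined to one holding criterion, so the change should be made but is not a reason to stop the trial.

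**What to change.** For doses still to be given, without a new scheduled visit:

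1. Reword the laboratory rule to count the same Grade 3 laboratory result first found at any scheduled visit up to and including the day-14 visit after ChAdOx1 85A, or the 7-day visit after MVA85A, and still Grade 3 on a repeat taken more than 48 hours later.
2. Make that repeat mandatory for every Grade 3 result, as soon as practicable after 48 hours. The table above shows what is lost if it slips to 96 hours.
3. Add 4 mL of chemistry to the existing day-2 draw in groups 5 and 6.

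**Cost.** A few repeat samples and 4 mL more blood per volunteer, so that the 3 mL/kg limit applies below 34 kg. There will be somewhat more holds, partly because the reworded rule also counts events that begin between days 7 and 14. Chemistry events that begin after day 2 and resolve before day 14 are still missed; for 7-day events the chance of a hold stays below 2% even at a true rate of 40%.

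A day-7 visit with chemistry would see more: under the same onset assumption, that sample alone documents 71% of 7-day events with a repeat at 48 hours and 43% with a repeat at 96 hours. It adds a visit and a further draw, so it is an option for the sponsor and DSMB to weigh and not part of the minimum change.
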